7. RESEARCH QUESTION AND OBJECTIVES

7.1. Safety Specifications

7.1.1. Important Identified Risks

(1) Liver disorder including venoocclusive liver disease (VOD)/sinusoidal obstruction syndrome (SOS)*

Rationale: In global Phase 3 (B1931022) and non-Japanese Phase 1/2 (B1931010) studies in patients with relapsed or refractory ALL, VOD/SOS frequently occurred, and grade ≥ 3 hepatotoxicity was also reported in the inotuzumab ozogamicin group. Hence, the occurrence of adverse drug reactions (ADRs) and other relevant matters after marketing will be examined in the special investigation.

(2) Myelosuppression

Rationale: In Study B1931022, myelosuppression occurred in the inotuzumab ozogamicin group, and many of these events were grade ≥ 3 . Hence, the occurrence of ADRs and other relevant matters after marketing will be evaluated in the special investigation.

(3) Infections

Rationale: In Study B1931022, infections occurred in many patients in the inotuzumab ozogamicin group, and infections attributable to myelosuppression would be likely to frequently develop. Hence, the occurrence of ADRs and other relevant matters after marketing will be assessed in the special investigation.

(4) Hemorrhage

Rationale: In Study B1931022, hemorrhage occurred in the inotuzumab ozogamicin group, and hemorrhage attributable to myelosuppression would be likely to frequently develop. Hence, the occurrence of ADRs and other relevant matters after marketing will be examined in the special investigation.

(5) Tumor lysis syndrome

Rationale: In Study B1931022, tumor lysis syndrome occurred in the inotuzumab ozogamicin group, and many of these events were grade ≥ 3 . Hence, the occurrence of ADRs and other relevant matters after marketing will be evaluated in the special investigation.

(6) Infusion reaction

Rationale: In Study B1931022, infusion reaction related to inotuzumab ozogamicin occurred in the inotuzumab ozogamicin group. Hence, the occurrence of ADRs and other relevant matters after marketing will be assessed in the special investigation.

(7) Pancreatitis

Rationale: In Studies B1931022 and B1931010, and Studies B1931006 and B1931008 involving subjects other than patients with relapsed or refractory ALL, pancreatitis occurred in the inotuzumab ozogamicin group. Pancreatitis may affect the benefit-risk balance of inotuzumab ozogamicin.

PFIZER CONFIDENTIAL

CT24-WI-JPN-GPSP01-RF09 8.0 Non-Interventional Study Protocol Template for Secondary Data Collection

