7.2. Research Objectives

The following matters will be investigated in patients receiving BESPONSA under actual conditions of use after marketing:

(1) Occurrence of adverse events (AEs) (including the following evaluations):

Background characteristics possibly affecting the onset of liver disorder including VOD/SOS, myelosuppression, infections and hemorrhage, and grade ≥ 3 events based on the CTCAE v4.0 as well as risk factors for early death of HSCT patients after BESPONSA treatment

(2) Efficacy (hematologic remission rate and survival)

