8.8.14. Adverse Events

Pertinent to safety assessment, the status of AEs during the period from the start of BESPONSA treatment to the end date of the observation period in the treatment phase (Day 28 post-treatment) will be confirmed, and the following information will be entered. For VOD/SOS, events during a period from the start of BESPONSA treatment to the end date of the observation period in the follow-up phase will be entered. When an AE is observed, the investigator should take an appropriate therapeutic action and promptly notify it to the sponsor. When the AE is related to BESPONSA, its course should be followed up until the AE or its sequelae resolve or become stable to the extent that is acceptable for the investigator and sponsor.

Also, further investigation should be separately conducted, if deemed necessary by sponsor for patients who experienced a serious adverse reaction, an unexpected adverse reaction or other adverse reactions not listed in the package insert.

- (1) Presence/absence of AE
- (2) Name of AE
- (3) Date of occurrence
- (4) CTCAE v4.0 Grade (worst grade)
- (5) Intervention
- (6) Seriousness
- (7) Outcome at the present
- (8) Causal relationship

Note: An AE is any and all unfavorable event (including clinically significant abnormal laboratory change) occurring in a patient after starting BESPONSA treatment regardless of causal relationship. A serious adverse event (SAE) is any unfavorable medical occurrence that results in death, is life-threatening, requires (or prolongs) hospitalization, causes persistent or significant disability/incapacity, results in congenital anomalies or birth defects, or is other conditions which represent significant health

PFIZER CONFIDENTIAL

Inotuzumab

B1931024 NON-INTERVENTIONAL STUDY PROTOCOL

Amended 8, 12 December 2023

hazards.

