8.12.2. Analysis Methods

8.12.2.1. Analysis of Safety Endpoints

The occurrence of ADRs will be tabulated. In addition to an analysis using the entire safety set, analyses in subgroups stratified according to patient background characteristics will be carried out. The occurrence of liver disorder including VOD/SOS, myelosuppression, infections, hemorrhage, tumor lysis syndrome, infusion reaction, pancreatitis, interstitial lung disease, QTc interval prolonged, inflammatory gastrointestinal events and reproductive toxicity will be tabulated. For patients with special background characteristics such as children, elderly patients, pregnant women, patients with renal impairment and patients with hepatic dysfunction, the occurrence will be tabulated. Risk factors related to the development of VOD/SOS and risk factors related to early death of HSCT patients after BESPONSA treatment will be assessed.

The details of the analysis plan are specified in the SAP.

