10.2. Reporting Period

For each patient, the period of safety event reporting in CRF (see the table above) begins at the time of the patient's first dose of BESPONSA, and lasts through the end of the observation period (this refers to the end date of observation period in the treatment phase) of the study, but the reporting period to Pfizer Safety must include at least 28 calendar days following the last dose of BESPONSA; a report must be submitted to Pfizer Safety (or its designated representative) for any of the types of safety events listed in the table above occurring during this period. If a patient was receiving BESPONSA on the last day of the observation period, then the reporting period should be extended for 28 calendar days following the end of observation period.

During the VOD/SOS reporting period, all VOD/SOS occurred before the end date of the observation period in the follow-up phase shall be reported as SAEs regardless of the causal relationship and severity.

If the investigator becomes aware of a SAE occurring at any time after completion of the study (this refers to the end date of the observation period in the treatment phase) and s/he considers the SAE to be related to BESPONSA, the SAE also must be reported to Pfizer Safety.

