10.3. Causality Assessment

The investigator is required to assess and record the causal relationship. For all AEs, sufficient information should be obtained by the investigator to determine the causality of each AE. For AEs with a causal relationship to BESPONSA, follow-up by the investigator is required until the event and/or its sequelae resolve or stabilize at a level acceptable to the investigator, and Pfizer concurs with that assessment.

An investigator's causality assessment is the determination of whether there exists a reasonable possibility that BESPONSA caused or contributed to an AE. If the investigator's final determination of causality is "unknown" and s/he cannot determine whether BESPONSA caused the event, the safety event must be reported within 24 hours.

If the investigator cannot determine the etiology of the event but s/he determines that BESPONSA did not cause the event, this should be clearly documented on the CRF and the NIS AEM Report Form.

PFIZER CONFIDENTIAL

CT24-WI-JPN-GPSP01-RF09 8.0 Non-Interventional Study Protocol Template for Secondary Data Collection

Study 01-Nov-2023

Page 26 of 33

Inotuzumab

B1931024 NON-INTERVENTIONAL STUDY PROTOCOL

Amended 8, 12 December 2023

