## **2.2. Study Objectives**

*To investigate the following items in patients treated with this drug under post-marketing routine uses.*

*[1] Occurrence of adverse events, including the investigation of following factors:*

*Background factors that may affect the occurrence of liver disorder including VOD/SOS, myelosuppression, infection, hemorrhage, and Grade  $\geq 3$  events based on Common Terminology Criteria for Adverse Events (CTCAE) version 4.0; and risk factors for early death in HSCT recipients after treatment with this drug.*

*[2] Effectiveness (hematologic response rate, survival)*

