For ADRs that occurred in at least 10% of patients, number and proportion of patients with the ADRs will be summarized for each SOC and PT by category of timing of initial onset [ $< 4$  weeks after the start of treatment,  $\geq 4$  weeks to  $< 8$  weeks,  $\geq 8$  weeks to  $< 12$  weeks,  $\geq 12$  weeks to  $< 16$  weeks,  $\geq 16$  weeks to  $< 20$  weeks,  $\geq 20$  weeks to  $< 24$  weeks,  $\geq 24$  weeks].

In addition, time to event will be summarized as per Section 8.1.4 with event being the first onset of the AR. The analysis will be performed with the following specifications:

- Analysis set: SAS
- Handling of patients with no AR: Censored at 28 days after the final dose of this drug.
- Time points for rate estimation: Weeks 1, 2, 3, 4, 8, 12, 16, 20, and 24
- **Occurrence of adverse drug reactions by inclusion/exclusion in the safety analysis set**

For the population of patients whose case report form was collected, a listing of ADRs in patients excluded from the SAS will be prepared. In addition, excluded patients with ADRs will be summarized by SOC and PT.

- **VOD/SOS**

Events of VOD/SOS reported as AR will be analyzed. Events included in each analysis will not be limited to events of initial onset. Unless otherwise specified, VOD/SOS events will be summarized respectively for each of the following categories.

- VOD/SOS that occurred after the start of this drug (Use the SAS as the analysis set.)
- VOD/SOS that occurred with absence of HSCT after the start of this drug (Same as above): Here, "absence of HSCT" means that VOD/SOS occurred with no HSCT or occurred before any HSCT.
- VOD/SOS that occurred with presence of HSCT after the start of this drug (Patients in the SAS who underwent HSCT after the start of this drug will be analyzed)

**Occurrence of VOD/SOS:** The number of patients with VOD/SOS and its proportion will be summarized. Among the factors listed in "Details of adverse drug reactions" in Section 8.2.3.1, n and proportion will be summarized with respect to each of the following factors: Action taken [discontinuation, temporary suspension or dose reduction, none], Outcome [fatal, not recovered, recovered with sequelae, recovering, resolved/recovered, unknown], CTCAE Grade (1) [1, 2, 3, 4, 5, unknown], and CTCAE Grade (2) [ $< 3$ ,  $\geq 3$ , unknown].

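### The VOD/SOS occurrence, onset-timing and risk-factor analyses in SAP 8.2.3.1 count only events judged drug-related; no all-causality risk ratio or time-to-onset estimate is planned beside them

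*SAP*

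**What the plan says.** **The aim.** Protocol 7.2, under the heading of adverse event occurrence, asks for "Background characteristics possibly affecting the onset of liver disorder including VOD/SOS, myelosuppression, infections and hemorrhage". SAP 2.2 repeats it: "Background factors that may affect the occurrence of liver disorder including VOD/SOS, myelosuppression, infection, hemorrhage". Protocol 8.12.2.1 says that "Risk factors related to the development of VOD/SOS and risk factors related to early death of HSCT patients" will be assessed. None of the three limits the VOD/SOS question to drug-related events. Protocol 8.10.2 and SAP 2.1 base the sample size on it.

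**The data.** Protocol 10.2 has every VOD/SOS case up to the end of follow-up sent in; these "shall be reported as SAEs regardless of the causal relationship and severity". Protocol 8.8.14 puts onset date, grade and causal relationship on the case report form. SAP 8.2.3 defines collection windows for VOD/SOS both as ADRs and as AEs.

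**The analysis.** SAP 8.2.3.1 then states "Events of VOD/SOS reported as AR will be analyzed". SAP 6.1 makes an ADR an AE that the physician considers causally related. The rest of the VOD/SOS block follows: the onset analysis censors patients without an ADR, and the factor analysis gives risk ratios and tests for the ADR.

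**What is planned on an all-causality basis.** The SAE table by SOC and PT (SAP 8.2.3.2), and a listing of patients with VOD/SOS adverse events (SAP 9).

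**The concern.** The planned outcome is VOD/SOS combined with a physician's attribution, while the stated question is about VOD/SOS. A case judged unrelated is moved to the non-cases in the factor analysis. In the onset analysis the same patient is censored at discontinuation or at the last observation date, so time after the event is also counted as event-free.

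This is more than lost events if attribution depends on the factor studied. Where a patient has had HSCT after starting the drug, or has a history of liver disease, the physician has another explanation to weigh. The outcome definition would then be shaped in part by the exposure, and the ADR-only risk ratio would not estimate the effect of the factor on VOD/SOS itself. This bears on the question the study was sized to answer. The documents give neither the direction nor the size of any such dependence.

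**Working it through.** **1. Is the gap filled elsewhere in the SAP?**

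- SAP 8.2.3.2 should count every VOD/SOS case, because each is reported as an SAE, but it gives only n and proportion.
- The SAP 9 listing shows the CRF items (causality among them), risk factors and onset times for each VOD/SOS patient. With the factor denominators in SAP 8.2.2, a reader could rebuild a crude risk ratio by hand. The listing covers cases only, so it holds no censoring dates for event-free patients.
- SAP 8.2.3.5 allows further analyses but commits to none.

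So no all-causality risk ratio with interval and test, and no all-causality time-to-event estimate, is planned.

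**2. Reproduce the plan's figure.** Inputs from Protocol 8.10.2: overall incidence 12.3%, relative risk 3.0, 1:1 split of 176 (88 per group), two-sided chi-square test at 0.1.

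- Risks: p_H = 3 p_L and p_H + p_L = 2 × 0.123, so p_L = 0.0615 and p_H = 0.1845.
- Standard errors: under the null √(2 × 0.123 × 0.877 / 88) = 0.0495; under the alternative √[(0.1845 × 0.8155 + 0.0615 × 0.9385) / 88] = 0.0486.
- Power = Φ[(0.123 − 1.645 × 0.0495) / 0.0486] = Φ(0.85) = 0.804, which matches the stated 80.4%.
- Expected cases: 88 × 0.1845 = 16.2 and 88 × 0.0615 = 5.4, together 21.6.

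**3. Effect of attribution on the risk ratio.** Let s_H and s_L be the shares of VOD/SOS judged related in the high- and low-risk groups. Then observed RR = 3.0 × s_H / s_L, and expected ADR cases = 16.2 s_H + 5.4 s_L. All shares are assumed, and 12.3% is read as an all-causality rate, which the documents do not state.

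| s_H | s_L | Observed RR | Expected ADR cases |
|---|---|---|---|
| 1.00 | 1.00 | 3.00 | 21.6 |
| 0.95 | 1.00 | 2.85 | 20.8 |
| 1.00 | 0.95 | 3.16 | 21.4 |
| 0.90 | 1.00 | 2.70 | 20.0 |
| 1.00 | 0.90 | 3.33 | 21.1 |
| 0.60 | 0.90 | 2.00 | 14.6 |
| 0.90 | 0.60 | 4.50 | 17.9 |

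With equal shares of 0.9, 0.8 or 0.7 the RR stays at 3.0 and the cases fall to 19.5, 17.3 or 15.2.

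**4. The same in whole cases.** With a and b cases in two groups of 88, RR = a/b and the 95% CI is exp[ln RR ± 1.96 √(1/a + 1/b − 2/88)].

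| Cases (high vs low) | Reading | RR (95% CI) | Fisher p |
|---|---|---|---|
| 16 vs 5 | all cases counted | 3.20 (1.23–8.36) | 0.018 |
| 14 vs 5 | two high-risk cases judged unrelated | 2.80 (1.05–7.44) | 0.050 |
| 16 vs 4 | one low-risk case judged unrelated | 4.00 (1.39–11.49) | 0.008 |
| 16 vs 3 | two low-risk cases judged unrelated | 5.33 (1.61–17.66) | 0.003 |

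With about 5 cases in the low-risk group, reclassifying one or two moves the estimate visibly, though every shifted value lies inside the first row's interval.

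**The case against.** **The ADR basis has support in the protocol.** For VOD/SOS, Protocol 7.1.1 says "the occurrence of adverse drug reactions (ADRs) and other relevant matters after marketing will be examined in the special investigation", and Protocol 8.12.2.1 opens with tabulation of ADRs. The factor analyses in SAP 8.2.3.4 are ADR-based too, and the revision history shows AEs being removed there, so the convention looks deliberate. On that reading, drug-related VOD/SOS is a legitimate target and the ADR risk ratio is not biased for it. This stands as a reason to keep the ADR analysis. It does not answer the objective, which carries no causality condition.

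**The argument would extend to the other listed risks.** Myelosuppression, infection and hemorrhage fall under the same objective and are also analysed as ADRs. That is true. VOD/SOS differs because the study was sized on it and because Protocol 10.2 requires its reporting whatever the causality through follow-up.

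**The effect may be nil.** The causality criterion is broad, a "reasonable possibility that BESPONSA caused or contributed to an AE", so nearly all cases may be judged related. That stands; the two versions would then agree, and showing so would be useful.

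**The timing is late.** SAP version 6.0 (September 2024) postdates the planned database release (May 2024, Protocol 5), so an addition now is post hoc. This is a reason to date and label it. Under SAP 4.1 all p-values are descriptive, so no decision rule is disturbed.

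**Conclusion.** The concern holds. SAP 8.2.3.1 limits the whole VOD/SOS block to physician-attributed events, while the objective and the sample-size rationale concern VOD/SOS as such and the all-causality data are collected. The planned SAE counts and case listing do not replace a risk ratio with its interval and test, or an onset estimate.

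The size is unknown. A gap of 5 to 10 percentage points in attribution, with the other group at 100%, would move a true RR of 3.0 to between 2.70 and 3.33. The 60%/90% scenarios (2.0 or 4.5) mark a wide gap for which the documents give no evidence. If attribution does not depend on the factor, there is no shift. No loss of power is claimed: testing is exploratory, and the documents do not say whether 26/212 counts all VOD/SOS or only related cases. The change is advisable because the documents alone cannot show whether attribution matters, and the collected data can.

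**What to change.** In SAP 8.2.3.1, run the VOD/SOS occurrence, onset-timing and factor analyses also on all VOD/SOS adverse events regardless of causality, and report them beside the retained ADR version. For the all-causality onset analysis, apply the existing censoring rule to patients with no VOD/SOS event of any attribution. Add one table of the number and share of VOD/SOS events judged related, by factor level. SAP 8.2.3.4 can stay as it is.

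The cost is SAP wording and a rerun of existing programs on a wider event flag; nothing new has to be collected. The output is not trivial: the VOD/SOS section lists 30 factor definitions (17 general and 13 for VOD/SOS after HSCT), and SAP 8.2 calls for similar analyses in the consent-based sets. Many cells of the attribution table will be small. The two sets of results need clear labels, and the SAP should record when the all-causality set was added.

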- Peripheral blast count before conditioning for the first HSCT after the start of this drug [≤ 1000 /µL, > 1000 /µL, not performed]
- Myeloblast count before conditioning for the first HSCT after the start of this drug [≤ 50%, > 50%, not performed]
- Time from the date of final dose of this drug to the date of the first HSCT after the start of this drug [< 4 weeks, ≥ 4 weeks to < 8 weeks, ≥ 8 weeks to < 12 weeks, ≥ 12 weeks to < 16 weeks, ≥ 16 weeks]
- Treatment cycles [1 cycle, 2 cycles, 3 cycles, 4 cycles, 5 cycles, 6 cycles, > 6 cycles]
- Treatment cycles [≤ 3 cycles, ≥ 4 cycles]
- Dosing of > 1.8 mg/m^2 per cycle [absent, present] (Considered to be present, if there is a cycle of > 1.8 mg/m^2 per cycle during the treatment period.)
- Pregnancy [absent, present] \* Pregnancy during the treatment period. Limited to cases in which information on pregnancy is collected
- Best overall response [complete remission (CR) or complete remission with incomplete hematologic recovery (CRI), progression or relapse, indeterminate/other, not performed]
- Minimal residual disease (MRD) [negativity achieved, negativity not achieved, test not performed]
  - \* Irrespective of the result of best overall response.
- Best overall response and MRD [CR/CRI achieved and negativity achieved, CR/CRI achieved and negativity not achieved, progression/relapse and negativity achieved, progression/relapse and negativity not achieved] \* "Indeterminate/other" and "not performed" are excluded.
- Adverse drug reactions that occurred during the treatment period - liver disorder as a safety specification [absent, present]

Subgroup analyses of hematologic response and MRD will be performed for the following patient characteristics and other factors:

- Age [< 15 years, ≥ 15 to < 65 years, ≥ 65 years]
- Age [< 18 years, ≥ 18 to < 55 years, ≥ 55 years]
- Age [< 15 years, ≥ 15 to < 40 years, ≥ 40 years]
- Disease name [Relapsed CD22+ acute lymphocytic leukemia (ALL), refractory CD22+ ALL]
- Chromosome karyotype [normal, t (4;11), unknown]
- Chromosome karyotype [Philadelphia chromosome positive, negative, unknown]\* Philadelphia chromosome is considered positive if the chromosome karyotype is t(9;22).
- Hemoglobin level immediately before the start of this drug [< 10 g/dL, ≥ 10 g/dL, not performed]
- Platelet count immediately before the start of this drug [< 10 × 10^4/µL, ≥ 10 × 10^4/µL, not performed]

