**Timing of onset of VOD/SOS:** To analyze the timing of onset of VOD/SOS, summary statistics will be performed as per Section 8.1.1, for the following kinds of time.

- Time from the final dose of this drug: Time (weeks) from the final dose of this drug to the onset of VOD/SOS
- Time from HSCT: Time (weeks) from the first HSCT after the start of this drug to the onset of VOD/SOS. Only VOD/SOS events that occurred with presence of HSCT after the start of this drug will be included in this analysis (Similar limitation shall also apply to the analysis set).

Patients with VOD/SOS will be counted by each of the following timing factors. For each timing factor, data will also be summarized in a histogram (The longitudinal axis is frequency. The width of each onset period will depend on the actual duration of the period).

- Time from the final dose of this drug: < 2 weeks, ≥ 2 weeks to < 4 weeks, ≥ 4 weeks to < 8 weeks, ≥ 8 weeks to < 12 weeks, ≥ 12 weeks to < 16 weeks, ≥ 16 weeks
- Time from HSCT 1: < 2 weeks, ≥ 2 weeks to < 4 weeks, ≥ 4 weeks to < 6 weeks, ≥ 6 weeks to < 8 weeks, ≥ 8 weeks. This time is defined as the time starting from the first HSCT after the start of this drug.
- Time from HSCT 2: ≤ 3 weeks, > 3 weeks. This time is defined as the time starting from the first HSCT after the start of this drug.

Regarding the timing of onset of events described in "Timing of onset of adverse drug reactions" in Section 8.2.3.1, data will be analyzed with the following specifications.

- Analysis set: Patients who finished the survey (Patients who are recorded as discontinued in the "Record of continued/discontinued survey [treatment period]" in the case report form or patients for whom "Record of continued/discontinued survey [follow-up period]" in case report form is filled in. The latter means the survey is discontinued and completed for the patient.)
- Handling of patients who did not experience ADRs: If the survey had been discontinued for the patient, data shall be censored on the date of discontinuation based on the "Record of continued/discontinued survey" in the case report form; if the survey had been completed for the patient, data shall be censored on the last observation date defined in Section 7.
- Time points for rate estimation: Every 4 weeks from Week 4 to Week 52

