#### **8.2.4. Effectiveness analyses**

##### **8.2.4.1. Hematologic response**

For patients who achieved the following responses based on the best overall response of hematologic response, their proportion and its confidence interval will be determined as per Section 8.1.3. Patients who underwent no clinical assessment of hematologic response will also be included in the analysis, but another analysis in patients except them will also be performed.

- CR or CRi
- CR
- CRi

Cycles in which CR or CRi was achieved for the first time will be analyzed by determining the proportion of patients as per Section 8.1.2. The relevant cycle is determined based on the assessment date for which CR or CRi was determined and shall include the date of the most recent past dose of this drug. If the assessment date is 29 days after the last dose or later, however, the cycle should be determined to be post-treatment; the following categories will be used for this analysis.

- Cycle 1, Cycle 2, Cycle 3, Cycle 4, Cycle 5, Cycle 6, Cycle  $> 6$ , post-treatment

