### 9. LISTINGS

The following data will be listed in tabular form:

- All patients
- Off-label diseases
- Dosing records
- Reasons for completion/discontinuation of treatment \* Only for "other" reasons.
- Concomitant anti-malignant tumor agents
- Hematopoietic stem cell transplants (before and after the start of this drug)
- Patients with AEs
- Patients with ADRs
- Patients with ADRs who were excluded from the safety analysis
- ADRs with data deleted
- Patients with serious ADRs
- Patients with serious AEs
- Patients with AEs of VOD/SOS
- Patients with ADRs in the population with hepatic impairment

- Patients with ADRs in the population with renal impairment
- Elderly patients with ADRs
- Patients with ADRs by event included in the safety specification
- Laboratory test values

The descriptions included in the listing of "Off-label diseases" are as follows:

- Disease name (as recorded by the physician)
- ADRs

The descriptions included in the listing of "Dosing records" are as follows:

- Items in the "Record of the Treatment with This Drug" page of the case report form
- Number of treatment cycles of this drug
- Number of doses and total dose of this drug in each cycle
- Total dose amount of this drug

The descriptions included in the listing of "Reasons for completion/discontinuation of treatment" are as follows:

- Details of the "other" reasons for the completion/discontinuation of treatment

The descriptions included in the listing of "Concomitant anti-malignant tumor agents" are as follows:

- Drug code
- Drug name [code-based name]
- Drug name [generic name]
- Drug name (product name) [as per physician's description]
- Start date

The descriptions included in the listing of "Hematopoietic stem cells transplants (before and after the start of this drug)" are as follows:

- Disease name (as per physician's description), salvage line number, and presence/absence of resumption of this drug
- Items in the "Hematopoietic Stem Cell Transplant (before the start of the treatment with this drug)" page of the case report form
- Items in the "Hematopoietic Stem Cell Transplant (treatment and follow-up periods)" page of the case report form. In addition, the following items will also be presented:
  - Months (days) from the start of this drug to the day of transplant
  - Months (days) from the date of the final dose of this drug to the day of transplant

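### VOD/SOS onset is timed from the final dose although on-treatment events are included, so later dosing gives negative times; the interval to first HSCT has the same gap if the drug is resumed after transplant

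*SAP*

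**What the plan says.** **VOD/SOS onset.** SAP 8.2.3.1 defines the clock as "Time from the final dose of this drug: Time (weeks) from the final dose of this drug to the onset of VOD/SOS". The times get the SAP 8.1.1 statistics, which include mean, median and minimum, and are then classed, opening with "Time from the final dose of this drug: < 2 weeks, ≥ 2 weeks to < 4 weeks". The first category of events analysed is "VOD/SOS that occurred after the start of this drug (Use the SAS as the analysis set". The same section adds that analyses are not restricted to first onsets, and a second category covers events with no HSCT or before any HSCT. Events during treatment are therefore included.

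**Interval to HSCT.** SAP 5.4 defines the factor "Time from the date of final dose of this drug to the date of the first HSCT after the start of this drug", with classes that open "date of the first HSCT after the start of this drug [< 4 weeks, ≥ 4 weeks to < 8 weeks". It is tested for VOD/SOS after HSCT (8.2.3.1) and for early death after HSCT (8.2.3.3), and it is tabulated and plotted in 8.2.2.

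**Signs that dosing may continue.** The VOD/SOS summary uses "Action taken [discontinuation, temporary suspension or dose reduction, none" as its action categories. The HSCT and VOD/SOS listings in Section 9 carry "presence/absence of resumption of this drug", which is not defined.

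**A different anchor elsewhere.** To assign a first CR or CRi to a cycle, SAP 8.2.4.1 says the cycle "shall include the date of the most recent past dose of this drug".

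No section redefines the final dose relative to the event or the transplant, limits these summaries to events after it, or says what to do with a negative time.

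**The concern.** On the plain reading, the final dose is the last one the patient receives. An onset followed by another dose then has a time below zero. That value does not describe latency after dosing; its size reflects how much treatment came afterwards. It still enters the summary statistics, and it satisfies the < 2 weeks class, which has no lower bound. On-treatment onsets and onsets shortly after the end of treatment become indistinguishable there.

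The HSCT interval raises a sharper issue in principle. If a patient were dosed again after the transplant, the interval would be negative and the patient would be classed < 4 weeks. A factor meant to describe the gap before transplant would then depend on what happened after it. Such a patient also had to survive long enough to be dosed again, which bears directly on a comparison of early death. VOD/SOS and early death after HSCT are both named in the study objectives (Protocol 7.2, SAP 2.2).

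**Working it through.** **1. The plan's own figure.** Protocol 8.10.2 gives 80.4% power for 176 patients (88 per group) at two-sided 0.1. Take rates 18.45% and 6.15% (mean 12.3%, ratio 3.0).

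- SE under the null: √(2 × 0.123 × 0.877 / 88) = 0.0495
- SE under the alternative: √((0.1845 × 0.8155 + 0.0615 × 0.9385) / 88) = 0.0486
- Power: Φ((0.123 − 1.645 × 0.0495) / 0.0486) = 0.804. The rounded rates 18.5% and 6.2% give 0.802.

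The figure reproduces. The point does not depend on it, but it gives the expected number of cases: 0.123 × 176 = 21.6, about 22.

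**2. On-schedule dosing.** Inputs from Protocol 8.2: doses on Days 1, 8 and 15; Cycle 1 of 21 or 28 days; later cycles of 28 days. Assume onset on day 20, with dosing continued on schedule. The SAP time is (20 − final-dose day)/7. The preceding dose is day 15, so the gap from it is 5/7 = 0.7 weeks throughout.

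| Cycles | Final-dose day (Cycle 1 of 21 / 28 days) | SAP time, weeks |
|---|---|---|
| 2 | 36 / 43 | −2.3 / −3.3 |
| 3 | 64 / 71 | −6.3 / −7.3 |
| 4 | 92 / 99 | −10.3 / −11.3 |
| 6 | 148 / 155 | −18.3 / −19.3 |

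Every value falls in < 2 weeks. So does 0.7. The longest on-schedule gap between doses is Day 15 to Day 29, 14 days, so an onset between doses is under 2 weeks from the preceding one. The values are wrong as latencies, but the class does not change.

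**3. When the VOD/SOS class changes.** Assume a gap, then onset, then resumption 4 weeks after onset with the final dose 2 weeks after that. The SAP time is −(4 + 2) = −6 weeks, in < 2 weeks. Measured from the preceding dose, onsets at 3, 5 and 9 weeks belong in 2 to < 4, 4 to < 8 and 8 to < 12 weeks.

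**4. HSCT interval.** Assume a last dose 12, 20 or 30 weeks after HSCT. The SAP interval is −12, −20 or −30 weeks, always < 4 weeks. If the last pre-transplant dose was 6, 10 or 14 weeks before HSCT, the right classes are 4 to < 8, 8 to < 12 and 12 to < 16 weeks. At 3 weeks the class is unchanged.

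**5. What wrong entries could do (all counts assumed).**

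- If 4 of 22 onset times are recorded as −5 instead of +1 week, the mean falls by 4 × 6 / 22 = 1.1 weeks.
- Suppose early deaths are 3/12 with a short gap and 2/14 with a longer one: 25.0% / 14.3% = 1.75. Move four re-dosed survivors to the short class: 3/16 against 2/10, or 18.8% / 20.0% = 0.94.

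**6. Internal check on the graphics.** SAP 8.2.2 starts the histogram of time from drug start to HSCT at 0 and treats the final-dose interval the same way. A negative interval would count in the < 4 weeks table row but have no histogram bar. The VOD/SOS histogram sets bar width by the length of each period, and < 2 weeks has no defined length once negative times occur.

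**The case against.** The strongest reply has five parts.

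- **Classes mostly hold.** On-schedule events stay in < 2 weeks under either anchor. This stands, and it removes most of the classification concern for VOD/SOS.
- **Dosing after VOD/SOS is inferred.** The action categories come from the general ADR list, and no action also fits an onset after treatment has ended. This stands in part. The SAP retains suspension and dose reduction as categories for VOD/SOS and includes on-treatment events without restriction, so a rule is needed.
- **Re-dosing after HSCT is thinly supported.** Resumption is an undefined listing item with no stated order relative to transplant. Protocol 8.8.1 records previous participation, so a later course might be a separate record. Protocol Table 1, as extracted, leaves unclear whether dosing in follow-up is captured. The histogram starting at 0 suggests that non-negative intervals were intended. This stands: the HSCT part is conditional.
- **Other outputs show the timing.** Onset from the start of treatment is unaffected. The individual graphs, with the last dose as origin, and the Section 9 listings would show onset before the last dose openly. All tests are exploratory (SAP 4.1). This limits the harm but does not correct the summary table.
- **Time from end of treatment is a legitimate measure, and the 8.2.4.1 anchor has another purpose.** Agreed, but a measure from end of treatment should then separate events that precede that end.

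**Conclusion.** The point holds in limited form. Followed literally, the SAP yields negative VOD/SOS onset times whenever a later dose is given. These distort the mean, median and minimum and mix on-treatment with early post-treatment onsets. For a day-20 onset the error runs from −2.3 against 0.7 weeks (two cycles) to −19.3 against 0.7 weeks (six cycles). With about 22 cases expected, a few such values matter. The HSCT interval has the same defect only if patients are dosed after their first transplant.

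A reader might infer more than the documents support:

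- **That VOD/SOS onsets are generally put in the wrong class.** They are not under on-schedule dosing. A class error needs a dosing gap followed by resumption, at a frequency the documents do not give.
- **That an effect of a short drug-to-HSCT gap on early death is being hidden.** The reversal from 1.75 to 0.94 is arithmetic on assumed counts, and post-transplant resumption is neither described nor excluded.
- **That overall survival after the final dose needs a new origin.** Death cannot precede the final dose, so no negative time arises and no change is asked for there.

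The result rests on reading the final dose as the last dose received, which is the plain sense but is not spelled out.

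**What to change.** - **SAP 8.2.3.1:** measure VOD/SOS onset from the most recent dose on or before onset. Alternatively, keep the final dose as origin, report onsets before it as a separate class, and exclude them from the summary statistics.
- **SAP 5.4, 8.2.2, 8.2.3.1 and 8.2.3.3:** measure the HSCT interval from the last dose before the first HSCT.
- **Reporting:** give the number of patients dosed after VOD/SOS onset and the number dosed after first HSCT. If the second is zero, the HSCT part has no effect on the results.
- **Definition:** state what resumption means in the listings and whether it can follow HSCT.

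The cost is SAP wording and a small change to date derivations. Protocol 8.8.3 collects dosing dates, so no new data should be needed; the team should confirm that the dosing record extends past the treatment phase where the drug was resumed. Patients with no dose after onset or after HSCT keep the same values. If the first option is taken for VOD/SOS, the tables should be relabelled, because time since the last preceding dose is a different quantity from time since the end of treatment.
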